6.3 Safety Assessments

6.3.1 Extent of Exposure

Depending on the clinical considerations for which parenteral opioid therapy is warranted, a patient could receive oliceridine using clinician-administered bolus dosing or PCA dosing. Patients will have the method of administration categorized as PCA if they received at least 1 PCA dosing. Otherwise the method of administration will be categorized as bolus.

Duration is defined as the difference in total hours from the first dose to the last dose of study medication.

6.3.2 Adverse Events

Adverse events includes any newly occurring event or previous condition that increased in severity or frequency from time of informed consent. AEs occurring from time of informed consent to the follow-up phase will be recorded in source documentation and will also be recorded in the EDC system if the patient receives oliceridine. All AEs must be recorded irrespective of whether or not they are considered medication-related. All AEs that are possibly or probably related to study medication will be followed until resolution or database lock, whichever occurs first. Changes in intensity or frequency of AEs should be recorded as separate events (i.e., a new record started).

Treatment emergent adverse events (TEAEs) are defined as AEs with onset at the time of or following the start of treatment with study medication until 7 days after the last dose of study medication or any pre-existing AEs that have worsened in severity on or after the first dose of study medication and through 7 days after the last dose of study medication.

Adverse events will be designated as treatment-emergent according to the following algorithm:

- If both the start date and start time of an AE are known, then:
- If the AE starts at any time prior to the time of the first dose on Day 1, then the AE will not be designated as treatment-emergent and hence will not be summarized.
- If the AE starts on or after the time of the first dose on Day 1 through 7 days after the last dose, then the AE will be designated as treatment-emergent.
- If only the start date of an AE is known and the start time of the AE is unknown, then:
- If the AE starts on Day 0, then the AE will not be designated as treatment-emergent and hence will not be summarized.

Client: Trevena, Inc.
 Version #: 1.0
 Version Date: 20Dec2016

Protocol/CIP #: CP130-3003

- If the AE starts on Days 1 through 7 days after the last dose, then the AE will be designated as treatment-emergent.

All AEs will be assessed on two descriptive parameters: intensity and relationship to the study medication:

- Intensity refers to the severity of an event and its impact on a patient's functioning. The following categories will be used to classify intensity:

Mild	Awareness of sign or symptom, but easily tolerated
Moderate	Discomfort enough to cause interference with usual activity
Severe	Incapacitating with inability to work or perform usual activity

- Relationship refers to the likelihood that the event being assessed was caused by the study medication. The following categories will be used to classify relationship:

Not Related	There is no reasonable association between the study treatment and the suspected event.
Unlikely Related	It is doubtful that there is an association between the study treatment and the suspected event. The event could have been produced by the patient's clinical state or other modes of therapy administered to the patient.
Possibly Related	The suspected AE may or may not follow a reasonable temporal sequence from study treatment administration. The event could have been produced or mimicked by the patient's clinical state or by other modes of therapy concomitantly administered to the patient.
Probably Related	The suspected AE follows a reasonable temporal sequence from study treatment administration, abates upon discontinuation of the treatment, and cannot be reasonably explained by the known characteristics of the patient's clinical state.

For summaries by relationship, possibly and probably related will also be combined into one "related" summary.

Client: Trevena, Inc.
 Version #: 1.0
 Version Date: 20Dec2016

Protocol/CIP #: CP130-3003

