4.1.4.1 Severity Rating

Each AE will be classified according to the following criteria:

Mild	Awareness of sign or symptom, but easily tolerated.
Moderate	Discomfort enough to cause interference with usual activity.
Severe	Incapacitating with inability to work or perform usual activity.

An AE that is assessed as severe should not be confused with a SAE. An event is defined as “serious” when it meets one of the predefined outcomes as described in [Section 4.1.2](#).

When changes in the intensity of an AE occur more frequently than once a day, the maximum intensity for the experience should be noted. If the intensity category changes over a number of days, those changes should be recorded separately (with distinct onset dates).

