4.2 Reporting Procedures and Requirements

4.2.1 Adverse Events

AEs occurring from time of informed consent to the follow-up phase will be recorded in source and will also be recorded in eCRF if the patient receives oliceridine. All AEs must be recorded irrespective of whether they are considered medication-related. All AEs that are potentially related to IP will be followed until resolution or database lock, whichever occurs first. This includes any newly occurring event or previous condition that has increased in severity or frequency from time of informed consent.

Any AEs already documented at a previous assessment and designated as ongoing should be reviewed at subsequent visits as necessary. If these have resolved, this should be documented. Changes in intensity or frequency of AEs should be recorded as separate events (ie, a new record started).

The investigator should report all AEs on the AE page(s) of the eCRF and source documents, regardless of seriousness, severity, and causality. Whenever possible, an AE will be reported using a diagnostic term, (eg, “common cold” or “upper respiratory infection” rather than “runny nose, cough, mild fever”) and should be described with the attributes described in [Section 4.1](#).

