8.6.3. Adverse Events

The MedDRA version 19.0 will be used to classify all verbatim AE terms with respect to SOC and PT. Summaries will include only TEAEs and will be summarized for the Safety Analysis Set for each cumulative dose group and for all groups combined.

An overall summary of TEAEs will be performed with the following categories: any TEAE, serious TEAEs, TEAEs with the outcome of fatal, and TEAEs leading to early discontinuation. Severity rating and relationship to study medication categories will also be summarized. The summary will include unique patient counts and percentages based on the number of patients in the cumulative dose group, and the total event count. Overall summary of TEAEs will be repeated by sex, age grouping 1, age grouping 2, race, median baseline NPRS score, BMI, CYP2D6 metabolizer status and initial setting subgroups.

The number and percentage of patients with TEAEs for each cumulative dose group and overall will also be displayed by SOC and PT and will be repeated by BMI and CYP2D6 metabolizer status subgroups. These 3 summary tables will also be repeated for serious TEAEs and TEAEs leading to early discontinuation.

TEAEs will also be summarized by PT only. This summary table will be repeated by BMI and CYP2D6 metabolizer status subgroups.

TEAEs, serious TEAEs and TEAEs resulting in early discontinuation will be summarized by cumulative dose and cumulative time based on the time point intervals defined in section 6.2.4. TEAEs by cumulative dose and cumulative time based on the time point intervals will also be summarized by PTs.

A summary of most common TEAEs will be presented, where PTs occurring in at least 5% of the all treated patients group will be included. Summaries will be sorted by PT in descending frequency in the all treated patients column.

Summaries of TEAEs by maximum severity (mild, moderate, or severe) will be performed by SOC and PT. Patients with missing severities will be counted as severe. Summaries of TEAEs by maximum relationship will be performed by SOC and PT. Patients with missing relationship will be counted as probably related.

The denominator for percentages will be the number of patient within the cumulative dose group for the Safety Analysis Set. The total number of events will be presented

Client: Trevena, Inc.
Version #: 1.0
Version Date: 20Dec2016

Protocol/CIP #: CP130-3003

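### The SAP 6.3.2 algorithm makes a pre-dose AE that eases after dosing a TEAE, against the SAP's own definition; separately, multi-day intensity changes inflate event counts but not patient counts

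*SAP*

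**What the plan says.** **Recording.** AEs are collected from informed consent, so a treated patient can have AE records that predate the first dose. SAP 6.3.2 then says "Changes in intensity or frequency of AEs should be recorded as separate events (i.e., a new record started", and Protocol 4.2.1 has the same rule. Neither restricts it to worsening.

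**Re-grading within a day.** Protocol 4.1.4.1 is narrower: "When changes in the intensity of an AE occur more frequently than once a day, the maximum intensity for the experience should be noted". For slower changes it says: "If the intensity category changes over a number of days, those changes should be recorded separately (with distinct onset dates".

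**TEAE definition.** SAP 6.3.2 counts AEs that begin from the first dose to 7 days after the last, and "any pre-existing AEs that have worsened in severity on or after the first dose of study medication" within the same period.

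**TEAE algorithm.** The steps that follow use only when the record starts. With date and time known, the condition for a TEAE is "If the AE starts on or after the time of the first dose on Day 1 through 7 days after the last dose". With the time missing, a Day 1 date is enough, and SAP 7.3.1 imputes the first-dose time.

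**Counting.** The overall summary in SAP 8.6.3 gives unique patients "and the total event count". The table shells label [E] as the number of events and count a patient once per system organ class and preferred term.

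**The concern.** The definition asks whether a pre-existing AE got worse. The algorithm cannot ask that, because it has no step that links a record to an earlier one or compares intensities. Since the recording rule opens a new record on improvement as well, an AE that eased after dosing arrives in the data as a record with a post-dose start, and the algorithm designates it a TEAE. A programmer has to follow one text or the other, and the choice changes the result.

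AE incidence is the measure for the primary objective (Protocol 1.3.1 and 2.1), and every patient receives oliceridine (SAP 4.3), so no control arm carries the same inflation. A wrongly designated record enters the patient count for its preferred term if the patient has no true TEAE for that term. It can also count toward the 5% cut for the most common TEAEs.

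The recording rule has a second, lesser consequence: no text merges the records of one episode before events are totalled.

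**Working it through.** The plan states no figure to reproduce. The check applies the written rules to hypothetical AE courses and counts TEAE events in three ways:

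- (i) the recording rule of SAP 6.3.2 and Protocol 4.2.1, with the SAP algorithm;
- (ii) the same, with Protocol 4.1.4.1 collapsing more than one change in a day to the maximum;
- (iii) the SAP's worsening definition, with consecutive records of one episode taken as one event.

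| Course | (i) | (ii) | (iii) |
|---|---|---|---|
| Moderate before dose, mild 1 h after | 1 | 1 | 0 |
| Moderate before dose, mild next day | 1 | 1 | 0 |
| Mild before dose, moderate 1 h after | 1 | 1 | 1 |
| Onset after dose: mild, moderate, mild over 3 days | 3 | 3 | 1 |
| Onset after dose: mild, moderate, mild within 1 day | 3 | 1 | 1 |

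**Rows 1 and 2** are the contradiction: 1 TEAE by the algorithm, 0 by the definition. Protocol 4.1.4.1 does not remove it, because a single change in a day is not more than one change a day, so Protocol 4.2.1 still opens a record.

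**Row 3** shows that algorithm and definition agree when the AE worsens.

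**Row 4** inflates [E] from 1 to 3. The patient is still counted once in the preferred-term row under all three readings.

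**Row 5** gives 3 events or 1 depending on which protocol section a site follows.

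**Choice of comparator for a repair.** Take an AE that is severe after surgery, mild just before dosing and moderate after dosing. Against the last pre-dose record it worsened (moderate exceeds mild) and meets the SAP definition. Against the highest pre-dose intensity it did not (moderate is below severe) and would be lost. The comparison has to be with the last pre-dose record.

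**Illustration of size (assumed inputs).** Let N = 1000 be the approximate planned number treated (SAP 4.4), q the share with one pre-dose AE that eases after dosing, and p the share of those with another TEAE anyway. The documents give neither q nor p. Take q = 1% to 10% and p = 30% to 60%.

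- Extra TEAE events = N × q: 1000 × 0.01 = 10, to 1000 × 0.10 = 100.
- Extra patients with at least one TEAE = N × q × (1 − p).
  - At q = 1%: 1000 × 0.01 × 0.4 = 4, to 1000 × 0.01 × 0.7 = 7.
  - At q = 10%: 1000 × 0.10 × 0.4 = 40, to 1000 × 0.10 × 0.7 = 70.
- The range is 4 to 70 patients, or 0.4 to 7.0 percentage points.

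**The case against.** **The algorithm may be meant as a date rule applied under the definition.** SAP 6.3.2 opens by describing AEs as new events or conditions that increased, so one could read improvement out. That is a possible intention, but no step carries it out. The table shells do not settle it either: they point to SAP 6.3.3 for the TEAE definition, and that section covers laboratory evaluations.

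**Few such records may exist.** Protocol 4.1.1 keeps anticipated surgical or medical symptoms out of the AE record unless they exceed expectation. Ordinary post-anaesthetic nausea may therefore have no pre-dose record to split. This stands. It limits the size but does not remove the contradiction.

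**Protocol 4.1.4.1 may be the specific rule that qualifies 4.2.1.** That is a fair reading for several changes in one day, and it then gives one event. It leaves a single same-day change and changes over several days untouched, and the documents do not say which section governs.

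**The consequence is limited.** No inferential testing is planned. Over-inclusion fits the SAP's other cautious conventions (missing severity counts as severe, missing relationship as probably related). The AE listing shows intensity and times, so easing records can be traced. All true, but the summary tables would still report an incidence that the definition does not support.

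**A stronger reading that does not hold.** A reader might infer that waxing and waning also raises patient-level incidence. It does not: patients are counted once per system organ class and preferred term, and the severity table takes the highest grade. Only [E] is affected. Nor is every later record caught, because TEAE status ends 7 days after the last dose.

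**Conclusion.** The point holds in two parts of unequal weight.

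First, SAP 6.3.2 contradicts itself on pre-existing AEs. Followed as written, the algorithm designates as treatment-emergent an AE that improved after the first dose. This can reach patient-level n (%) when the patient has no other TEAE for that term. The contradiction follows from the text alone.

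Its size does not. The 4 to 70 patients rest wholly on the assumed 1% to 10% and 30% to 60%, and Protocol 4.1.1 may push the true number down. A reader might infer a definite bias of several percentage points in nausea or similar terms, but the documents do not support any particular figure.

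Second, [E] counts intensity records rather than episodes when intensity changes over days. For changes within one day, it depends on which protocol rule the site followed. Patient counts are unaffected by this second part.

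**What to change.** In SAP 6.3.2, add a linking step. A post-dose record that continues a pre-dose record (same preferred term, contiguous dates) is a TEAE only if its severity exceeds that of the last record before the first dose. Say in the same place how a record opened for higher frequency at unchanged severity is treated, since the SAP names frequency in its AE description but not in its TEAE definition.

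For [E], collapse contiguous records of one episode to one event at maximum severity. Alternatively, keep the count and label it in the tables as a number of records.

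State in the SAP how records made under Protocol 4.1.4.1 and under 4.2.1 are reconciled for analysis. This avoids a protocol amendment. Aligning the two protocol sections themselves would need one, with renewed instruction to sites.

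The cost is a few lines of SAP text and a small programming step before database lock. The downside is a small risk of merging two separate episodes of the same term that happen to abut. The AE listing still shows the individual records.

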7.3.1. Adverse Events

If the AE stop date is completely missing and the AE has resolved, the stop date will be imputed as the date of the patient's last visit in the study.

- If only the year is known, the stop date will be imputed as “31-Dec” of that year or as the date of the patient's last clinic visit in the study if in the same year.
- If the month and year are known, the stop date will be imputed as the last day of that month unless the stop date corresponds to the same month as the patient's last clinic visit in which case the date of patient's last clinic visit in the study will be used instead.

If the start date is completely missing it will be imputed as follows:

- If the stop date occurs on or after the start of study medication or the event is ongoing, the start date will be imputed as the date of the first dose of study medication.
- If the stop date occurs before the start of study medication, the start date of the event will be imputed as the patient's screening date or the stop date of the event, whichever the earlier.

If the start time is missing it will be imputed only in the case where the start date of the event corresponds to the date of the first dose of study medication. In this case the time will be imputed as the same time as the first dose of study medication. In all other cases the time will not be imputed. Imputed dates will be used for calculations, however the actual date collected will be presented in listings.

Chiltern, International – Confidential

Page 20 of 30

Chiltern, International, All rights reserved. Reproduction or transmission to others apart from the parties involved with this document in any form or by any means is not permitted without the prior written consent of Chiltern, International.

Client: Trevena, Inc.
 Version #: 1.0
 Version Date: 20Dec2016

Protocol/CIP #: CP130-3003

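### The SAP's TEAE algorithm omits the worsening limb of its own definition, so a timed pre-dose AE that worsens after dosing is dropped whenever the worsening stays on the original record

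*SAP*

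**What the plan says.** SAP 6.3.2 gives a definition with two limbs. An AE is treatment-emergent if it begins at or after the start of treatment, up to 7 days after the last dose. The second limb adds "any pre-existing AEs that have worsened in severity on or after the first dose of study medication", over the same period.

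The SAP then says AEs will be designated by an algorithm. Where start date and time are both known, an AE that "starts at any time prior to the time of the first dose on Day 1, then the AE will not be designated as treatment-emergent", and it is left out of the summaries. Where only the date is known, "If the AE starts on Days 1 through 7 days after the last dose, then the AE will be designated as treatment-emergent". SAP 7.3.1 agrees for a missing time on the date of first dose: "In this case the time will be imputed as the same time as the first dose of study medication". No branch mentions worsening.

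Three recording rules bear on this:
- SAP 6.3.2, just before the definition: "Changes in intensity or frequency of AEs should be recorded as separate events (i.e., a new record started". Protocol 4.2.1 says the same.
- Protocol 4.1.4.1, for changes within a day: "When changes in the intensity of an AE occur more frequently than once a day, the maximum intensity for the experience should be noted".
- Protocol 4.1.4.1, for longer changes: "If the intensity category changes over a number of days, those changes should be recorded separately (with distinct onset dates".

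SAP 8.6.3 restricts the AE summaries to TEAEs.

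**The concern.** The definition and the algorithm are meant to be the same rule, but only the definition includes worsening. The algorithm is the part a programmer will code. AEs are collected from informed consent (Protocol 4.2.1) and again in the predose period (Protocol 3.1.3), so timed pre-dose records will exist.

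AE incidence is the main safety measure (Protocol 1.3.1). A record dropped here is absent from the overall, serious, discontinuation, preferred-term and maximum-severity tables alike. It carries its maximum intensity with it, so the missing event may be a severe one. Two programmers, one coding the definition and one the algorithm, could produce different tables from the same data.

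**Working it through.** The plan states no figure to reproduce. The study is single-arm and descriptive, so no power or error-rate formula applies. The check has three steps.

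**Step 1. Apply both rules to test histories.** Take the first dose at 09:00 on Day 1 (an illustrative time).

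| AE history | Record start(s) | Algorithm | Definition | Result |
|---|---|---|---|---|
| A. Starts 07:00 Day 1, no worsening | 07:00 | no | no | agree |
| B. Starts 07:00, worsens 11:00 Day 1, new record | 07:00; 11:00 | no; yes | yes | agree |
| C. As B, but one record at maximum intensity | 07:00 | no | yes | event lost |
| D. Starts 07:00 Day 1, worsens Day 2, own onset date | Day 1; Day 2 | no; yes | yes | agree |
| E. Starts Day -1, worsens 11:00 Day 1, new record | Day -1; 11:00 | no; yes | yes | agree |
| F. As E, but one record | Day -1 | no | yes | event lost |
| G. Begins pre-dose on Day 1, time unknown, no worsening | Day 1 | yes | no | over-counted |
| H. Starts Day -1, time unknown, no worsening | Day -1 | no branch applies | no | rule missing |

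Only C and F lose a worsened event. H arises because the algorithm names a Day 0, while the numbering in SAP 6.2.3 goes from -1 to 1.

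**Step 2. Ask when C or F can arise.** F needs a site to depart from the recording rules, since a change across days gets its own onset date. C is less clear. Protocol 4.1.4.1 contrasts changes within a day (note the maximum) with changes over several days (record separately). A site could reasonably keep an AE that changes several times on Day 1 as one record. Protocol 4.2.1 and SAP 6.3.2 point the other way. A single step up on Day 1 falls outside the literal wording of the within-day rule, so the new-record rule governs it.

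**Step 3. Size.** Patients losing that TEAE = N x p x s, where N is about 1000 (SAP 4.4), p is the share of patients with a pre-dose AE that worsens after dosing, and s is the share of those kept on the original record. The documents give neither p nor s; both are assumed.

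| p | s = 0 | s = 0.5 | s = 1 |
|---|---|---|---|
| 0.5% | 0 | 2.5 | 5 |
| 1% | 0 | 5 | 10 |
| 2% | 0 | 10 | 20 |
| 5% | 0 | 25 | 50 |

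For example, 1000 x 0.05 x 1 = 50. Any other TEAE in these patients would still count.

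**The case against.** The strongest defence is that the algorithm works record by record and relies on the new-record rule printed in the same section. Where sites follow that rule, every worsening has a post-dose start and passes. This stands, and it is why the lower bound is 0. It is also true that Protocol 4.1.4.1 never states that only one record is kept, that the analysis involves no testing, and that AE Listing 16.2.5.1 would still show the event.

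The defence does not remove the contradiction in the text, and the SAP does not say that the algorithm depends on new records. The listing is a weak safeguard. Its shell has no treatment-emergent flag, and it shows one intensity with start and end times, so a reader could not tell when the intensity rose.

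A reader might infer three stronger things that the documents do not support:
- *That every AE beginning before the first dose is dropped.* Day 1 AEs with an unknown start time are counted, even if they began before dosing.
- *That the loss can be sized from phase 2 nausea.* The 18% placebo rate in Protocol 1.1 is an outcome after abdominoplasty, not the frequency of AEs recorded before a first dose. This study also enrols medical and ED patients. Protocol 4.1.1 keeps anticipated symptoms in surgical or medical patients from being recorded unless they exceed what is expected.
- *That reported incidence is biased downward on balance.* History G errs upward, and the net direction is not established.

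**Conclusion.** The point holds in a limited form. The algorithm is wrong as written because it leaves out half of the definition it implements. The practical loss is confined to AEs with a known pre-dose start date and time whose worsening was not given a new record, most plausibly those with several intensity changes on Day 1. The size is unknown: 0 under full use of new records, and any upper figure, including the 50 per 1000 above, is an assumption. The severity is moderate to minor. No stated figure is wrong, but the rule feeds the main safety tables and should be settled before database lock.

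**What to change.** 1. In SAP 6.3.2, replace the first known-time bullet with: *An AE that starts before the first dose is not treatment-emergent unless its severity increased on or after the first dose and through 7 days after the last dose.*
2. Reconcile Protocol 4.1.4.1 with 4.2.1 by stating that the same-day maximum-intensity rule does not span the first dose. Any increase in severity after the first dose then opens a new record with its own start time. Item 1 depends on this, because one intensity with start and end times cannot show when worsening occurred.
3. For single Day 1 records ongoing at the first dose, where the timing of the maximum intensity cannot be determined, count them as TEAEs in a sensitivity summary. Do not move them automatically into the main tables. Some will have peaked before dosing and never worsened, and counting those would itself breach the definition.

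While editing, correct the Day 0 reference, and correct the mock-display footnotes that cite SAP 6.3.3 (clinical laboratory evaluations) for the TEAE definition.

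The cost is a short protocol and eCRF clarification, a little extra programming and one added summary. Reported incidence may rise slightly.
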